7.1.2. QTc Stopping Criteria

The *same* Fridericia QT correction formula (QTcF) correction formula *must* be used for *each individual participant* to determine eligibility for and discontinuation from the study. This formula may not be changed or substituted once the participant has been enrolled.

- The Baseline QTcF should be based on averaged QTcF values of triplicate electrocardiograms obtained over a brief (e.g., 5-10 minute) recording period from the Day 1 pre-dose ECG.
- A randomized participant that develops an on-treatment QTcF >500 msec or an increase from baseline QTcF >60 msec should have two repeat unscheduled ECG's within 10 minutes. Using these triplicate ECGs, if the average QTcF >500 msec or an increase from baseline QTcF >60 msec, the participant will be withdrawn from the study. Finally, this participant should have repeated unscheduled ECGs until their QTcF measurement returns to their original averaged QTcF value at Day 1 pre-dose.

See the SoA (Section [1.3](#)) for data to be collected at the time of treatment discontinuation and follow-up and for any further evaluations that need to be completed.

7.1.3. Columbia Suicide Severity Rating Scale Criteria

Emergence of any positive (abnormal) response confirmed by the investigator on a clinician (or qualified designee) administered C-SSRS during the on-treatment phase of the study will be cause for discontinuation of study intervention.

Refer to the SoA (Section [1.3](#)) for data to be collected at the time of intervention discontinuation and follow-up and for any further evaluations that need to be completed.

7.1.4. Individual Participant Laboratory Abnormality and Adverse Event Stopping Criteria

Investigators should make every effort to have a discussion with the medical monitor before the next dose to help assess if the study intervention should be stopped.

- Any clinically significant AE deemed to require discontinuation of study intervention
- Any Grade 3 or higher rash or Grade 2 rash with evidence of systemic involvement
- Any allergic or hypersensitivity reactions to either or both drugs
- Any Grade 3 or higher psychiatric AE
- New onset suicidal ideation
- Any Grade 3 or higher AE related to study intervention
- Any Grade 4 AE or laboratory abnormalities (with the exception of an asymptomatic Grade 4 cholesterol, triglyceride, or CPK increase)

7.2. Participant Discontinuation/Withdrawal from the Study

- A participant may withdraw from the study at any time at his/her own request, or may be withdrawn at any time at the discretion of the investigator for safety, behavioral, compliance, or administrative reasons. This is expected to be uncommon.
- A subject who is withdrawn from the study for any reason related to safety (listed in Section 7.1.4 or otherwise) will be continued to be followed to assess the outcome of the safety event that triggered discontinuation of study drug.
- At the time of discontinuing from the study, if possible, an early discontinuation visit should be conducted, as shown in the SoA. See SoA (Section 1.3) for data to be collected at the time of study discontinuation and follow-up and for any further evaluations that need to be completed.
- The participant will be permanently discontinued both from the study intervention and from the study at that time.
- If the participant withdraws consent for disclosure of future information, the sponsor may retain and continue to use any data collected before such a withdrawal of consent.
- If a participant withdraws from the study, he/she may request destruction of any samples taken and not tested, and the investigator must document this in the site study records.

7.3. Lost to Follow Up

A participant will be considered lost to follow up if he or she repeatedly fails to return for scheduled visits and is unable to be contacted by the study site.

The following actions must be taken if a participant fails to return to the clinic for a required study visit:

- The site must attempt to contact the participant and reschedule the missed visit as soon as possible and counsel the participant on the importance of maintaining the assigned visit schedule and ascertain whether or not the participant wishes to and/or should continue in the study.
- Before a participant is deemed lost to follow up, the investigator or designee must make every effort to regain contact with the participant (where possible, 3 telephone calls and, if necessary, a certified letter to the participant's last known mailing address or local equivalent methods). These contact attempts should be documented in the participant's medical record.
- Should the participant continue to be unreachable, he/she will be considered to have withdrawn from the study.

Discontinuation of specific sites or of the study as a whole are handled as part of [Appendix 4](#).

8. STUDY ASSESSMENTS AND PROCEDURES

- Study procedures and their timing are summarized in the SoA (Section 1.3).
- Protocol waivers or exemptions are not allowed.
- Immediate safety concerns should be discussed with the sponsor immediately upon occurrence or awareness to determine if the participant should continue or discontinue study intervention.
- Adherence to the study design requirements, including those specified in the SoA, is essential and required for study conduct.
- All screening evaluations must be completed and reviewed to confirm that potential participants meet all eligibility criteria. The investigator will maintain a screening log to record details of all participants screened and to confirm eligibility or record reasons for screening failure, as applicable.
- Procedures conducted as part of the participant's routine clinical management (e.g., blood count) and obtained before signing of ICF may be utilized for screening or baseline purposes provided the procedure met the protocol-specified criteria and was performed within the time frame defined in the SoA.
- The maximum amount of blood collected from each participant over the duration of the study, including any extra assessments that may be required, will not exceed 500 mL.
- Repeat or unscheduled samples may be taken for safety reasons or for technical issues with the samples.

8.1. Efficacy Assessments

Not applicable.

8.2. Safety Assessments

Planned time points for all safety assessments are provided in the SoA (Section 1.3).

8.2.1. Physical Examinations

- A full physical examination will include, at a minimum, assessments of the skin, cardiovascular, respiratory, GI, and neurological systems. Height and weight will also be measured and recorded.
- A brief physical examination will include, at a minimum, assessments of the skin, lungs, cardiovascular system, and abdomen (liver and spleen).
- Investigators should pay special attention to clinical signs related to previous serious illnesses.

8.2.2. Vital Signs

- Oral temperature, pulse rate, respiratory rate, and blood pressure will be assessed.
- Blood pressure and pulse measurements will be assessed in the semi-recumbent position with a completely automated device. Manual techniques will be used only if an automated device is not available.
- Blood pressure and pulse measurements should be preceded by at least 5 minutes of rest for the participant in a quiet setting without distractions (e.g., television, cell phones).
- Vital signs (to be taken before blood collection for laboratory tests) will consist of 3 blood pressure and pulse measurements (3 consecutive blood pressure and pulse readings will be recorded at intervals of at least 1 minute). Each measurement will be recorded in the case report form (CRF).

8.2.3. Electrocardiograms

- On Day 1 of both Period 1 and Period 2, triplicate ECGs will be taken prior to dosing. The ECGs should be recorded over a brief (e.g., 5 to 10 minutes) recording period. Each measurement will be recorded in the CRF.
- Single 12-lead ECG will be obtained at other time points as outlined in the SoA (Section 1.3) using an ECG machine that automatically calculates the heart rate and measures PR, QRS, QT, and QTcF intervals. Refer to Section 7.1.2 for QTcF withdrawal criteria and additional QTcF readings that may be necessary.
- Twelve-lead ECGs will be performed with the participant in a supine or semi-supine position after a rest of at least 10 minutes.
- At each time point at which triplicate ECG are required, 3 individual ECG tracings should be obtained as closely as possible in succession, but no more than 2 minutes apart. The full set of triplicates should be completed over a brief (e.g., 5 to 10 minutes) recording period.

8.2.4. Clinical Safety Laboratory Assessments

- Refer to [Appendix 2](#) for the list of clinical laboratory tests to be performed and to the SoA (Section [1.3](#)) for the timing and frequency.
- The investigator must review the laboratory report, document this review, and record any clinically relevant changes occurring during the study in the AE section of the CRF. The laboratory reports must be filed with the source documents. Clinically significant abnormal laboratory findings are those which are not associated with the underlying disease, unless judged by the investigator to be more severe than expected for the participant's condition.
- All laboratory tests with values considered clinically significantly abnormal during participation in the study or within 7 days after the last dose of study intervention should be repeated until the values return to normal or Baseline or are no longer considered significantly abnormal by the investigator or medical monitor.
- If such values do not return to normal/baseline within a period of time judged reasonable by the investigator, the etiology should be identified and the sponsor notified.
- All protocol-required laboratory assessments, as defined in [Appendix 2](#), must be conducted in accordance with the laboratory manual and the SoA.

8.2.5. Suicidal Risk Monitoring and Management of Emergent Psychiatric Symptoms

GSK3640254 is not a central nervous system active drug nor is it being developed for a neurologic or psychiatric condition. However, given the risk of suicidal ideation identified with previous MI GSK3532795, all participants will undergo screening using the C-SSRS administered by a clinician (or qualified designee); any positive (abnormal) response confirmed by the investigator, will exclude them from participating. A repeat assessment will be done at the end of the treatment phase of the study. In case of positive (abnormal) response confirmed by the investigator, the participant will discontinue from the trial and the investigator will arrange for urgent specialist psychiatric evaluation and management.

As described in Section [7.1.4](#), new onset suicidal ideation at any time will result in immediate discontinuation from the trial and the investigator will arrange for urgent specialist psychiatric evaluation and management.

The definitions of behavioral suicidal events used in this scale are based on those used in the Columbia Suicide History Form [[Posner, 2007](#)]. Questions are asked on suicidal behavior, suicidal ideation, and intensity of ideation. Screening visit questions will be in relation to lifetime experiences and current experiences (within the past 2 months) and all subsequent questioning in relation to the last assessment.

Emergent non-suicidal psychiatric AE Evaluation and Management:

- Any Grade 1 or 2 psychiatric AE: A Grade 1 or 2 psychiatric AE may result in additional unscheduled visits (in-clinic or at home) as clinically indicated. This may include a more in-depth assessment of AE through interview, additional

unscheduled clinical labs, and/or imaging. Psychiatric consultation may be required at the discretion of the investigator. Any pharmacotherapy should be discussed with the medical monitor.

- Any Grade 3 or 4 psychiatric AE: As described in Section 7.1.4, a Grade 3 or 4 psychiatric AE will result in discontinuation from the trial and emergency psychiatric evaluation (including potential hospitalization and pharmacotherapy as indicated).

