	Day -1	Day 1-5	Day 6-9	Day 1-5	Day 6	Day 7	Day 1	Day 2	Day 3	Day 4	Day 5	Day 6	Day 7	Day 8	Day 9	Day 10 ¹	Day 11	
Study intervention: Dolutegravir 50 mg		X					X	X	X	X	X	X	X					
Study intervention: GSK3640254 200 mg				X	X	X	X	X	X	X	X	X	X					
DTG trough PK sampling		D2-4						X	X	X	X	X						Blood collection for DTG trough PK samples will be collected on Days 2 through 4 in Period 1, Days 2 through 6 in Period 3.
DTG serial PK sampling		D5	D6-8										X	X	X	X		Blood collection for PK analysis of DTG will be collected pre-dose, and after dosing at 1, 1.5, 2, 3, 3.5, 4, 4.5, 5, 6, 8, 12, 24, 48, and 72 hours relative to Day 5 dosing in Period 1, and relative to Day 7 dosing in Period 3.
GSK3640254 trough PK sampling				D 4-5	X					X	X	X						Blood collection for GSK3640254 trough PK samples will be collected on, Days 4 through 6 in Period 2; and Days 4 through 6 in Period 3.

Procedure	Period 1		W	Period 2			Period 3							Follow-up				Notes
	Day -1	Day 1-5	Day 6-9	Day 1-5	Day 6	Day 7	Day 1	Day 2	Day 3	Day 4	Day 5	Day 6	Day 7	Day 8	Day 9	Day 10 ¹	Day 11	
GSK3640254 serial PK sampling						X	X						X	X	X	X	X	Relative to Day 7 dosing in Period 2, blood for PK analysis of GSK3640254 will be collected predose, and after dosing at 1, 2, 2.5, 3, 3.5, 4, 4.5, 5, 6, 8, 12, and 24 hours. Relative to Day 7 dosing in Period 3, the PK samples will be collected at predose, and after dosing at 1, 2, 2.5, 3, 3.5, 4, 4.5, 5, 6, 8, 12, 24, 48, 72, and 96 hours.
AE review	←=====→																	
SAE review	←=====→																	
Concomitant medication review	←=====→																	

AE = adverse event; D = Day; DTG = dolutegravir; ECG = electrocardiogram; PK = pharmacokinetic; SAE = serious adverse event; W = washout.

1 Evaluations scheduled for Day 10 in Period 3 will also be performed for participants who discontinue early.

- The timing and number of planned study assessments, including safety, pharmacokinetic (PK), or other assessments may be altered during the course of the study based on newly available data (e.g., to obtain data closer to the time of peak plasma concentrations) to ensure appropriate monitoring.

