Neurologic/psychiatric safety	
Two psychiatric serious adverse events in previous maturation inhibitor GSK3532795 clinical program (acute psychosis, homicidal/suicidal ideation) were seen at suprathreshold doses in healthy subjects in the thorough QT (TQT) study.
 
From a neurologic and psychiatric AE summary and pharmacokinetic/pharmacodynamic analysis for GSK3532795 across all studies mild Grade 1 headache and Grade 1 sleep abnormalities were the predominant AEs, with a trend for increasing neurologic and psychiatric AEs with increasing dose (based on TQT and Phase 2b studies). No exposure-response relationship was seen for select neurologic and psychiatric AEs (based on TQT and Phase 2b studies). Central nervous system penetration data for GSK3532795 and GSK3640254 in rats demonstrate a similarly low
	
Screening: Protocol exclusion criterion based on any pre-existing psychiatric condition (including results of psychological assessment) for participants. Participants will have a clinician (or qualified designee) administered Columbia Suicide Severity Rating Scale (C-SSRS) and will be included given no positive (abnormal) response.
 
On-Treatment: Participants will undergo physical examinations and laboratory testing. In addition, participants will undergo continuous evaluation for AEs during their participation in the study; there are individual clinical stopping criteria based upon incidence and intensity of treatment-emergent AEs. Participants will be housed throughout study conduct to ensure rapid diagnosis and management of any potential event.

Potential Risk of Clinical Significance	Summary of Data/Rationale for Risk	Mitigation Strategy
	brain distribution/penetration.	
The C-SSRS will be administered during and/or after the treatment phase of the study. In the event of a positive (abnormal) response confirmed by the investigator, the participant will discontinue from the trial and the investigator will arrange for urgent specialist psychiatric evaluation and management. Guidance for the investigator on the management of emergent psychiatric symptoms will be available (see Section 8.2.5).
 
Finally, there are clinical stopping criteria based upon intensity of treatment-emergent psychiatric AEs (see Section 7.1.4).

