7. DISCONTINUATION OF STUDY INTERVENTION AND PARTICIPANT DISCONTINUATION/WITHDRAWAL

7.1. Discontinuation of Study Intervention

In rare instances, it may be necessary for a participant to permanently discontinue study intervention. If study intervention is permanently discontinued, the participant will remain in the study to be evaluated for safety. See the SoA (Section 1.3) for data to be collected at the time of discontinuation of study intervention.

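### Participants who stop early after repeated GSK3640254 dosing have no scheduled end-of-treatment C-SSRS; adding it to the early-discontinuation evaluations is a cheap, low-priority improvement

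*Protocol*

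**What the plan says.** Protocol Section 8.2.5 requires a C-SSRS at screening and then states: "A repeat assessment will be done at the end of the treatment phase of the study". Later forms are not lifetime questionnaires; the same section sets "all subsequent questioning in relation to the last assessment".

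The Schedule of Activities (Protocol Section 1.3, repeated in SAP Appendix 1) marks the C-SSRS at Screening, on Period 2 Day 1 and on Period 3 Day 7. It does not say whether the on-study forms come before or after that day's dose.

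For participants who stop, Section 7.1 sends the reader to the Schedule "for data to be collected at the time of discontinuation of study intervention". The Schedule answers in footnote 1: "Evaluations scheduled for Day 10 in Period 3 will also be performed for participants who discontinue early".

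Two stopping rules are relevant. Under Section 7.1.3, a confirmed positive C-SSRS "during the on-treatment phase of the study will be cause for discontinuation of study intervention". Section 7.1.4 separately lists "New onset suicidal ideation", and Section 8.2.5 adds that "new onset suicidal ideation at any time will result in immediate discontinuation from the trial". The risk table in Section 2.3.1 is less specific about timing: "The C-SSRS will be administered during and/or after the treatment phase of the study".

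**The concern.** Section 8.2.5 ties the repeat C-SSRS to the end of treatment, but the Schedule ties it to a calendar day that only participants still on study reach. For someone who stops early, treatment ends on another day, and the substitute set of evaluations omits the instrument. The C-SSRS record after repeated dosing, which the SAP plans to list (Appendix 9, display 2.19), is then guaranteed only for those who stay to the last dosing day.

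This matters somewhat because Section 2.3 names neuropsychiatric safety among the major risks of GSK3640254, and Section 8.2.5 gives the experience with the earlier maturation inhibitor as the reason for using the scale. Section 8.3.2 prefers open questions that do not lead the participant. The C-SSRS is the assessment that asks directly about ideation and behavior. A person leaving for another reason, such as a gastrointestinal event or a QTc finding, could go without being asked.

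**Working it through.** No formula applies beyond counting days. The check is to fix the calendar, place the forms on it, and read the evaluations given to early stoppers.

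**1. Calendar.** Inputs from Protocol Sections 1.3 and 4.1: screening 28 days, Period 1 5 days, washout 4 days, Period 2 7 days, Period 3 7 days, follow-up Days 8 to 11, which is 4 days. Section 4.3 gives no washout between Periods 2 and 3.

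28 + 5 + 4 + 7 + 7 + 4 = 55 days, which reproduces the stated study duration of about 55 days.

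**2. Form dates, counting Period 1 Day 1 as Day 1.**
- Period 2 Day 1: 5 + 4 + 1 = Day 10, GSK3640254 dose 1.
- Period 3 Day 1: 5 + 4 + 7 + 1 = Day 17, GSK3640254 dose 8.
- Period 3 Day 7: 5 + 4 + 7 + 7 = Day 23, GSK3640254 dose 14.

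The Period 2 Day 1 form follows at most one GSK3640254 dose. The Period 3 Day 7 form is the only scheduled one after repeated dosing.

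**3. Early stoppers.** Footnote 1 gives them the Period 3 Day 10 evaluations. In the SAP copy of the Schedule, that column carries a brief physical examination, vital signs, ECG, laboratory tests and a pregnancy test. The C-SSRS row has no mark on Day 10 or Day 11. Scheduled C-SSRS forms at the early-discontinuation evaluation: 0.

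The uncovered window runs from a last dose of number 2 to a last dose of number 13. This describes the calendar; it does not count people.

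**4. Look-back of the last form for completers.** 23 − 10 = 13 days, to the nearest day because time relative to dose is not given. With a form before dosing on Period 3 Day 1, this becomes 17 − 10 = 7 days on GSK3640254 alone and 23 − 17 = 6 days on the combination.

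**5. Reach of the Section 7.1.3 rule.** A positive form on Period 3 Day 7 can prevent at most 1 dosing day, or none if the form follows the dose. A positive form before dosing on Period 3 Day 1 could prevent up to 14 − 8 + 1 = 7 combination days, but only for ideation that began in Period 2.

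**The case against.** The strongest reply is that nothing in the plan is broken. The Period 3 Day 7 form satisfies Section 8.2.5 for those who reach it, and the timing in Section 2.3.1 is loose enough to be met. Participants with significant psychiatric history or a positive screening form are excluded. Those enrolled are housed throughout, with ongoing adverse event evaluation and a suicidal-ideation rule that does not wait for a form. Section 7.2 expects withdrawals to be rare and follows safety-related ones to outcome. Section 1.3 allows safety assessments to be added on emerging data.

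The background data also limit the weight. The two psychiatric serious events came from a related compound at supra-therapeutic doses. GSK3640254 was given for 14 days at 50 to 320 mg once daily with no psychiatric event among the Grade 2 or most frequent events listed. The single-dose part had one Grade 2 depression, judged unrelated, and Study 208131 had no psychiatric events.

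All of this stands, and it sets the priority low. It does not put a C-SSRS into the early-discontinuation evaluations.

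Three stronger readings are tempting and unsupported:
- A reader might infer that early stoppers get no C-SSRS at all. Anyone who reached Period 2 has the Period 2 Day 1 form, and someone who stops in Period 1 has had no GSK3640254. Section 7.1 also keeps a person who stops study intervention under safety evaluation, so a later form is possible, although Section 7.2 ends intervention and study together and footnote 1 requires only the Day 10 set.
- A reader might infer that suicidality goes unmonitored between forms. The any-time stopping rule and confinement contradict that. The one-dosing-day limit above describes a single form, not the protection participants have.
- A reader might infer that a missing Period 3 Day 1 form is a defect. Given those safeguards, it is nearer a preference.

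**Conclusion.** The point holds in a limited form. The repeat C-SSRS described for the end of treatment is not scheduled for a participant who stops after the second GSK3640254 dose and before the Period 3 Day 7 form. For that person, scheduled forms after repeated dosing number zero, against one for a completer. It is a gap in structured questioning, not an absence of monitoring, and no pharmacokinetic endpoint, estimate or sample size is touched.

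The number affected cannot be derived from the documents. The allowance of 16 − 12 = 4 participants covers every reason for being non-evaluable, so it is at most a loose ceiling for planning and not a forecast.

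The conclusion assumes that footnote 1 is the full list of what early stoppers receive, and that the Schedule's C-SSRS row is as it appears in both documents.

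**What to change.** Amend footnote 1 of the Schedule of Activities so that anyone who discontinues early after at least one GSK3640254 dose also has a C-SSRS, covering the time since the previous form, at the discontinuation evaluation. Repeat the change in SAP Appendix 1.

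The cost is one footnote and a few short interviews using an instrument and staff already in the trial: no more than 4 if the whole allowance of 4 were used up by such stops, which is an assumption. No visit or blood sample is added. Because dosing has already stopped, this form prevents no dosing; its value is detection and referral before the person leaves.

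Optional, and weaker: add a C-SSRS before dosing on Period 3 Day 1 and apply Section 7.1.3 before the first combination dose. This means up to 16 more interviews. A confirmed positive would cost that participant's Period 3 data, which both primary comparisons need. It would give no earlier warning of ideation that starts in Period 3. It also could not separate a dolutegravir effect from longer GSK3640254 exposure, because combination days are always GSK3640254 days 8 to 14.
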